More than 80% of hepatocellular carcinoma (HCC) patients are not candidates for curative treatments, such as resection or liver transplant, the outcome of HCC patients remained very poor. Recently, sorafenib—a multitarget tyrosine kinase inhibitor—was found to improve survival of patients with Child-Pugh A unresectable HCC. The median overall survival (OS) was 10.7 months for patients on sorafenib vs 7.9 months for placebo, $P = .0006$, and median time-to-progression (TTP) was 5.5 months for patients on sorafenib vs 2.8 months for placebo, ($P < 0.001$). Notably, out of all patients under the SHARP trial, 421 patients had extrahepatic spread (EHS) and/or macrovascular invasion (MVI) (Sorafenib=209, placebo=212). For patients with EHS and/or MVI (Sorafenib vs placebo), OS was 8.9 vs 6.7 months (HR: 0.77; 95% CI: 0.60, 0.99) and TTP was 4.1 vs 2.7 months (HR: 0.64; 95% CI: 0.48, 0.84). (Sherman M, et al. 44th ASCO Annual Meeting).

Considering that the cause of death of HCC patients with extrahepatic spread is mainly intrahepatic HCC progression or hepatic failure, rather than extrahepatic metastasis, the intentional addition of an intra-arterial local therapy modality, such as

Yttrium-90 microspheres, could offer added survival and quality of life benefit.
Surprisingly, no data have been available on this approach until now.

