2.3 Rationale for the Treatment of Hepatocellular Carcinoma

According to the American Cancer Society, primary liver cancer is a major health problem worldwide. [4] Globally, it is the fifth most commonly diagnosed cancer in men and eighth most common in women, with more than 700,000 new cases in 2007. It is the third leading cause of cancer death in men and sixth among women. In North America and Western or Northern Europe, areas with historically low rates, the incidence of liver cancer is increasing, possibly due to increased prevalence of hepatitis C.

In 2007, the US FDA approved sorafenib tosylate (Nexavar®), a small molecule Raf kinase and VEGF receptor kinase inhibitor, for the treatment of patients with unresectable hepatocellular carcinoma (HCC). [5] The approval was based on the results of an international, multicenter, randomized, double-blind, placebo-controlled trial (SHARP3 trial) in patients with unresectable, biopsy-proven hepatocellular carcinoma. [2] Overall survival was the primary efficacy endpoint. A total of 602 patients were randomized; 299 to sorafenib 400 mg twice daily and 303 to matching placebo.

Demographics and baseline disease characteristics were similar between the sorafenib and placebo groups. Prior treatments included surgical resections (20 %), locoregional therapies (including radiofrequency ablation, percutaneous ethanol injection and transarterial chemoembolization in 40 percent), radiotherapy (5 %), and systemic therapy (4 %).

The trial was stopped following a pre-specified second interim analysis for survival disclosing a statistically significant advantage for sorafenib [median 10.7 vs. 7.9 months; HR: 0.69 (95 percent CI: 0.55, 0.87), $p=0.00058$]. The final analysis of time-to-tumor progression (TTP) by independent radiological review was based on data from an earlier time point and demonstrated a statistically significant improvement in TTP in the sorafenib group [median 5.5 vs. 2.8 months; HR: 0.58 (95 % CI: 0.45, 0.74), $p=0.000007$].

Sorafenib is now suggested as the standard-of-care (SOC) therapy for patients with advanced HCC, the patients classified as BCLC C according to the Barcelona Clinic Liver Cancer (BCLC) classification system. [6] Sorafenib is included in the NCCN Clinical Practice Guidelines in Oncology (NCCN– Hepatobiliary cancers V.1.2010 – HCC5) as one of the possible treatments for patients with unresectable HCC and extensive liver disease who are not candidates for transplantation. [7]

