For those patients without the pre-treatment high risk factors noted above, TheraSphere is very well tolerated, with treatment in the US commonly administered in an outpatient setting. Hospitalization for treatment effects associated with TheraSphere administration is rare.

3. Study objectives

The objective of this study is to evaluate the safety of continuous sorafenib 400 mg twice daily followed, after 3-5 weeks, by Yttrium-90 treatment in patients with child-Pugh A, BCLC-stage C HCC.

Primary objective:

- Median progression-free survival (PFS)

Secondary objectives:

- Overall survival (OS)
- Time to radiographic progression (TTRP)
- To evaluate the safety of the combination of sorafenib and Yttrium-90; Adverse events (NCI-CTAE v 4.0)
-

[figure not shown]
Other objectives:

Predictive Biomarkers of response to therapy and survival: will assess pre-treatment plasma level of IGF-1 as above, and assess its predictive ability of TTP and OS

4. Study design

This is a single-arm phase II clinical trial to evaluate the safety of continuous sorafenib at 400 mg twice daily followed, after 4 (+/- 1 week) weeks from starting sorafenib, by Yttrium-90 treatment concomitant with sorafenib, in patients with child-Pugh A, BCLC-stage C HCC. Of note, the time between starting sorafenib and Yttrium-90 administration will be 4 weeks regardless whether the patient underwent dose reductions or interruptions. Patients will continue taking the maximum tolerating dose of sorafenib, with no interruption during and after the Yttrium-90 procedures. This is a single-institution study that will be conducted at MDACC, Department of GI Medical Oncology and Department of Interventional Radiology. No sorafenib interruptions around the procedure will be applied, and only one Y-90 treatment only will be performed.

Study schema:

5. Study population

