5.1.1 Inclusion criteria

1. Subjects must be able to understand and be willing to sign the written informed consent form. A signed informed consent form must be appropriately obtained prior to the conduct of any trial-specific procedure.
2. Male or female patients ≥ 18 years of age
3. Life expectancy of at least 12 weeks (3 months).
4. Patients with histological or cytologically documented HCC (Documentation of original biopsy for diagnosis is acceptable if tumor tissue is unavailable) or clinical diagnosis by AASLD criteria in cirrhotic subjects is required {Bruix, 2005}. For subjects without cirrhosis histological confirmation is mandatory.
5. Patients must have at least one tumor lesion that meets the following criteria: The lesion can be accurately measured in at least one dimension according to RECIST
6. The target lesion(s) has not been previously treated with local therapy (such as surgery, radiation therapy, hepatic arterial therapy, chemoembolization, radiofrequency ablation, percutaneous ethanol injection or cryoablation).
7. Patients who have received local therapy, such as surgery, radiation therapy, hepatic arterial embolization, chemoembolization, radiofrequency ablation, percutaneous ethanol injection or cryoablation are eligible if the previously treated lesions have progressed or recurred can be identified as target lesions. Local therapy must have been completed at least 4 weeks prior to the baseline scan.
8. Patients who have received Yttrium-90 microspheres are not eligible.
9. Patients who have an ECOG PS ≤ 1
10. Patients who are categorized under BCLC-C stage
11. Cirrhosis grade of Child-Pugh class A. Child-Pugh status should be calculated based on clinical findings and laboratory results during the screening period.
12. The following laboratory parameters:
 - a. Platelet count $\geq 60 \times 10^9/L$
 - b. Hemoglobin ≥ 8.5 g/dL
 - c. Total bilirubin ≤ 2.5 mg/dl
 - d. Alanine transaminase (ALT) and AST ≤ 5 x upper limit of normal
 - e. Serum creatinine ≤ 1.5 x the upper limit of normal
13. Prothrombin time (PT)-international normalized ratio (INR) ≤ 2.3 or PT ≤ 6 seconds above control.
14. All acute toxic effects of any prior treatment have resolved to NCI-CTCAE v4.0 Grade 1 or less at the time of signing the Informed Consent Form (ICF).

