5.1.2 Exclusion criteria

1. Main portal vein thrombosis (PVT)
2. Patients who are eligible for curative treatment (ablation or resection or transplantation)
3. Previous or concurrent cancer other than HCC unless without evidence of disease for 5 or more years prior to entry, except cervical cancer in-situ, treated basal cell carcinoma, or superficial bladder tumor.
4. Tumor replacement >70% of total liver volume based on visual estimation by the investigator OR tumor replacement >50% of total liver volume in the presence of albumin <3 mg/dL
5. Contraindications to angiography and selective visceral arterial catheterization
6. Any known contraindications to sorafenib including allergic reaction, pill-swallowing difficulty, uncontrolled hypertension or history of cardiac disease, significant GI bleed within 30 days, metastatic brain disease, renal failure requiring dialysis
7. Concomitant treatment or within 28 days of one of the following:
 - a. Any other systemic anticancer agent other than agents used for cancer prevention
 - b. Subjects who have used strong CYP3A4 inducers (eg, phenytoin, carbamazepine, phenobarbital, St. John's Wort [*Hypericum perforatum*], dexamethasone at a dose of greater than 16 mg daily, or rifampin [*rifampicin*], and/or rifabutin) within 28 days before treatment.
 - c. UGT 1A1 and UGT 1A9 substrates (e.g., irinotecan)
 - d. P-Gp substrates (e.g., Digoxin)
8. Prior radiation therapy to the liver
9. Prior systemic therapy for the treatment of HCC, including sorafenib
10. Any history of symptomatic pulmonary compromise, such as chronic obstructive pulmonary disease
11. Any prior intervention for, or ongoing compromise of, the Ampulla of Vater or biliary-enteric anastomosis.

12. Clinically evident ascites (trace ascites on imaging is acceptable)
13. Pregnant or breast-feeding patients
14. A positive serum pregnancy test within 14 days prior to treatment in women of childbearing potential
15. Uncontrolled hypertension (systolic pressure >140 mm Hg or diastolic pressure > 90 mm Hg [NCI-CTCAE v4.0] on repeated measurement) despite optimal medical management.
16. Active or clinically significant cardiac disease including:
 - a. Congestive heart failure – New York Heart Association (NYHA) > Class II.
 - b. Active coronary artery disease.
 - c. Cardiac arrhythmias requiring anti-arrhythmic therapy other than beta blockers or digoxin.

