8.1 Statistical and analytical plans

Statistical consideration for 2012-0870: study of sorafenib plus theraspheres for extrahepatic hepatocellular carcinoma (redesign, 20 patients have enrolled in study 2012-0870)

This is a phase II study of sorafenib plus theraspheres for extrahepatic hepatocellular carcinoma (EHC). The primary objective is to evaluate the progression-free survival (PFS), where the progression-free survival will be measured from the start of therapy until failure to disease progression or death.

Historical data showed that the median PFS was 4.1 months for EHC patients treated with sorafenib alone. We expect that the combination treatment would improve the PFS. A maximum of 40 will be recruited for the study at a rate of 1-2 patients per month. The study will monitor toxicity and futility.

Futility monitoring

The primary endpoint PFS will be monitored using the method of Thall et al. (2005), and we will stop enrolling patients to the study if, based on the available data, we have little reason to believe that the median PFS of the combination therapy (m_E) is more than that of sorafenib alone (m_S) in the historical data, which was 4.1 months. Formally, we'll stop the study early if

$$\text{Prob}(m_E > m_S | \text{data}) < 0.15$$

That is, if there is less than 15% chance the median PFS of the combination therapy is more than that of sorafenib, the trial will be stopped. Where m_S represents the median PFS for sorafenib alone in the historical data with an inverse gamma distribution $IG(11, 41)$, which corresponds to a mean of 4.1 months and a variance of 1.87. m_E represents the median PFS for the study combination therapy, assuming the prior for m_E is $IG(2.17, 4.8)$, which has the same mean as m_S but with a much larger variance (i.e. 99) to reflect much greater uncertainty about the median PFS of the combination therapy of sorafenib and theraspheres.

Futility monitoring will start once 20 patients have been enrolled. Assuming an accrual rate of 1.5 per month and an additional follow-up of 12 months, the operating characteristics for the futility stopping rule under various true states are summarized in the following table 8, with results based on 5000 simulations.

Table 8. Operating characteristics for the time-to-progression monitoring

True Median Time to progression	Pr(stop early)	Average Number of Patients Treated (25th, 75th percentiles)
2	0.993	21 (20, 20)
3	0.529	31.4 (20, 40)
4	0.100	38.3 (40, 40)

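### The 4.1-month sorafenib PFS benchmark in Section 8.1 has no source and matches only a time-to-progression figure, so the futility rule and the final comparison with sorafenib appear to mix two endpoints

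*Combined protocol and SAP*

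**What the plan says.** Section 8.1 makes PFS the primary endpoint: "progression-free survival will be measured from the start of therapy until failure to disease progression or death". Its benchmark is the sentence "Historical data showed that the median PFS was 4.1 months for EHC patients treated with sorafenib alone", with no reference attached.

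The number 4.1 is then used in four places in Section 8.1:
- The benchmark median mS has the distribution IG(11, 41), with mean 4.1.
- The prior for the combination's median mE, IG(2.17, 4.8), is given the same mean.
- Enrolment stops if P(mE > mS | data) falls below 0.15, with monitoring from 20 patients.
- The final analysis reports the posterior probability that the combination's median PFS exceeds that of sorafenib.

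Elsewhere, 4.1 months appears once. Section 1 reports, for sorafenib against placebo in the phase III subgroup with extrahepatic spread and/or macrovascular invasion, "TTP was 4.1 vs 2.7 months (HR: 0.64; 95% CI: 0.48, 0.84". Survival in the same subgroup is given as "OS was 8.9 vs 6.7 months (HR: 0.77; 95% CI: 0.60, 0.99". Section 2.3 gives the whole-trial TTP as "median 5.5 vs. 2.8 months; HR: 0.58".

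Section 3 lists "Time to radiographic progression (TTRP") as a secondary objective, separate from PFS. The title and first column of Table 8, and one sentence of the primary analysis, speak of time to progression although the endpoint being monitored is PFS.

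**The concern.** In a single-arm trial the historical benchmark does the work of the control arm. TTP, in its usual meaning, does not count deaths without progression; PFS does. If 4.1 months is the Section 1 TTP, deaths before progression count against the combination and not against sorafenib. Within one population median PFS cannot exceed median TTP, so to that extent the bar is too high.

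Two results depend on it: the decision to stop enrolment, and the only planned comparison with sorafenib. Both would then partly reflect the change of endpoint and not only the treatment.

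The population adds a second uncertainty. Eligibility is "Patients who are categorized under BCLC-C stage" (Section 5.1.1), extrahepatic spread is not required, and "Main portal vein thrombosis (PVT") is an exclusion (Section 5.1.2). The enrolled patients may therefore differ from the subgroup behind the 4.1.

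**Working it through.** **Inputs.** From Section 8.1: mS ~ IG(11, 41); mE prior IG(2.17, 4.8); stop if P(mE > mS | data) < 0.15; monitoring from 20 patients, maximum 40; 1.5 patients per month; 12 months of additional follow-up. From Section 1: subgroup TTP 4.1 and OS 8.9 months. From Section 2.3: whole-trial TTP 5.5 months. The document gives no sorafenib PFS, so the share of deaths before progression is an assumption and is shown as a range.

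**Step 1: reproduce the plan.** The mean of IG(a, b) is b/(a − 1), and 41/10 = 4.1. The variance is b²/((a − 1)²(a − 2)), and 1681/(100 × 9) = 1.87. For mE, 4.8/1.17 = 4.10, with variance 99. All agree with the plan.

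With exponential times, d events and total follow-up T, the posterior is mE ~ IG(2.17 + d, 4.8 + ln2 × T). The rule was simulated with a look at each enrolment from 20 and a last look 12 months after the final entry (40,000 runs).

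| True median (months) | Pr(stop), Table 8 | Pr(stop), reproduced |
|---|---|---|
| 2 | 0.993 | 0.994 |
| 3 | 0.529 | 0.531 |
| 4 | 0.100 | 0.103 |
| 5 | 0.017 | 0.017 |

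The arithmetic of the plan is sound for a 4.1-month benchmark. At a true median of exactly 4.1, Pr(stop) is 0.085.

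**Step 2: same population as the 4.1.** Let deaths before progression add a fraction x to the progression hazard. Under exponential times, median PFS = 4.1/(1 + x). To judge how large x might be, the all-death hazard relative to the progression hazard is 4.1/8.9 = 0.46. So x = 0.10, 0.20 and 0.30 put deaths before progression at 0.10/0.46 = 22%, 0.20/0.46 = 43% and 0.30/0.46 = 65% of the overall death rate.

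The table takes a combination whose true PFS equals that of sorafenib. Re-anchored means that the second parameter of both priors is divided by 1 + x. The mean final P(mE > mS) is taken with all 40 patients followed to the last look, ignoring any early stop.

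| x | True PFS (months) | Pr(stop), 4.1 bar | Pr(stop), re-anchored | Mean final P, 4.1 bar | Mean final P, re-anchored |
|---|---|---|---|---|---|
| 0.10 | 3.73 | 0.168 | 0.082 | 0.440 | 0.538 |
| 0.20 | 3.42 | 0.288 | 0.079 | 0.353 | 0.538 |
| 0.30 | 3.15 | 0.430 | 0.077 | 0.278 | 0.538 |

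**Step 3: the enrolled mix.** A PFS bar of 4.1 is right only if sorafenib TTP in the enrolled patients is 4.1 × (1 + x) = 4.51, 4.92 or 5.33 months. If their TTP is the whole-trial 5.5, then PFS = 5.5/(1 + x):

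| x | True PFS (months) | Pr(stop), 4.1 bar | Mean final P, 4.1 bar |
|---|---|---|---|
| 0.10 | 5.00 | 0.017 | 0.724 |
| 0.20 | 4.58 | 0.035 | 0.647 |
| 0.30 | 4.23 | 0.067 | 0.570 |

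Here the bar is too low. Across both cases the mean final P for a combination with no added benefit runs from 0.28 to 0.72, against 0.54 with a correct anchor.

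**The case against.** The strongest objection is that the mismatch is inferred. Section 8.1 labels the figure PFS, and its wording for the patients differs from Section 1 (extrahepatic disease, against extrahepatic spread and/or macrovascular invasion). An unreported PFS of 4.1 months cannot be excluded. This stands, and the claim goes no further than the match. A stopping threshold still needs a source either way.

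Second, no net bias is shown for the enrolled patients: the results above lie on both sides of the correctly anchored values. Other features also bear on the comparison. Section 5.2 calls patients who stop for reasons other than toxicity before Y-90 inevaluable and replaced, although it also says that no withdrawn subject is replaced. Table 7 places the first scheduled restaging at the end of cycle 3. These points stand. They limit any statement of direction, but they do not make the benchmark's endpoint any clearer.

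Third, mS is not fixed at 4.1: IG(11, 41) has median 3.84 and a 95% range of 2.23 to 7.47, and Table 8 already covers true medians from 2 to 5. But the spread of mS is included in every simulation above and does not correct a shifted centre. Table 8 varies the true median, not the anchor.

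Fourth, the size rests on x, and nothing in the document supports the 30% case in particular. That is fair. Defining the percentage instead as the share of PFS events that are deaths without progression (PFS = 4.1 × (1 − s)), and re-anchoring mS only, gives stopping of 0.175, 0.348 and 0.618 for 10%, 20% and 30%. The direction within the benchmark population is the same, but the size depends on the assumption.

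**Conclusion.** The concern holds as stated. It is established that the 4.1-month benchmark is uncited, that its only match in the document is a TTP, that no sorafenib PFS for this disease is given, and that the trial's own PFS counts deaths. That the 4.1 actually is the Section 1 TTP is an inference.

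If it is, then within that subgroup the false-futility probability rises from about 0.08 to between 0.17 and 0.43, assuming exponential times and a 10% to 30% addition to the progression hazard from deaths. For the BCLC-C patients actually eligible, the net effect could go either way. The use of time to progression for PFS in Table 8 and the primary analysis is loose wording and secondary. The point should be fixed, because the number sets both the stopping decision and the only comparison with sorafenib.

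**What to change.** Keep PFS as the primary endpoint.

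1. Cite the source of the 4.1 months and state whether it is PFS or TTP, and in which patients.
2. Unless it is a true PFS median, replace 4.1, IG(11, 41) and the matching mean of the mE prior with a sourced sorafenib PFS median for a comparable population. Choose it without reference to PFS in the 20 patients already enrolled.
3. Re-run Table 8 and the credible-interval statement that follows it.
4. If no PFS source exists, say that 4.1 is a TTP serving as an upper-bound benchmark for that subgroup, and show Table 8 and P(mE > mS) over a range of lower PFS anchors.
5. Write PFS for time to progression in Table 8 and in the primary analysis.

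The technical cost is one source check, wording in Section 8.1, one re-run of the design software and updated priors on the monitoring website. If the priors change, Section 11.1 also requires the agreement of Bayer and, where necessary, approval of an amendment by the ethics board. No patients, visits or procedures are added.

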- Patients who have received Yttrium-90 microspheres are not eligible.
- Patients who have an ECOG PS ≤ 1
- Patients who are categorized under BCLC-C stage
- Cirrhotic status of Child-Pugh class A. Child-Pugh status should be calculated based on clinical findings and laboratory results during the screening period.
- The following laboratory parameters:
 - Platelet count $\geq 60 \times 10^9/L$
 - Hemoglobin ≥ 8.5 g/dL
 - Total bilirubin ≤ 2.5 mg/dl
 - Alanine transaminase (ALT) and AST ≤ 5 x upper limit of normal
 - Serum creatinine ≤ 1.5 x the upper limit of normal
- Prothrombin time (PT)-international normalized ratio (INR) ≤ 2.3 or PT ≤ 6 seconds above control.

Plan for statistical analysis	
The primary analysis is to evaluate the toxicity profile, and the secondary analysis to assess the overall survival and progression-free survival. The study will be monitored for toxicity. Being descriptive in nature, this trial will not focus on hypothesis testing. Descriptive statistics will be computed for all continuous and categorical variables of interest. All statistical analyses will be performed using SAS (version 9.3; SAS Institute, Inc., Cary, NC). For the primary analysis, all patients received treatment will be included the analysis for toxicity. Continuous parameters will be summarized using descriptive statistics, such as number of patients, mean, standard deviation, median and range. The toxicities will be summarized with frequency and 95% confidence interval (95% CI) by type, severity and their relationship to the treatment. Assuming a 30% of grade 3 or 4 treatment related toxicity rate, with 20 patients, the 95% CI will be (9.9%, 50.1%).
 
For the secondary analysis, the Kaplan-Meier method will be applied to estimate the probabilities of overall survival and progression-free survival as well as the median OS duration and PFS duration. The Log rank test will be used to compare the two time-to-event outcomes between patient subgroups.

--------------------------------------	---

Imaging Requirements

- Triple Phase CT – To determine liver volume measurement, identify hepatic vascular anatomy to determine TheraSphere dosimetry
 - Spiral CT abdomen/pelvis –performed with cuts of 10 mm or less in slice thickness contiguously in the axial plane to assess hepatic and extra-hepatic lesions according to the RECIST 1.1 criteria.

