Additionally, we have accrued 20 patients on the current study with a primary aim to evaluate the safety of the combination of sorafenib and Yttrium-90; adverse events (NCI-CTAE v 4.0) and found no grade 4 or 5 reactions. A few grade 3 reactions occurred in the form of: liver enzymes increase (ALT=1 patient, AST=3 patients, and bilirubin = 1 patient), Fatigue (=2), and 1 patient for each of the following: encephalopathy, hypertension, hyponatremia, hypophosphatemia, thrombocytopenia, maculo-papular rash, weight loss and vomiting.

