6.2.1.2 Dose modification for hematologic toxicities

Recommended Dose Modification for Hematologic Toxicities [Table 2]

Toxicity	ANC/AGC (x 10 ⁹ /L)	Hemoglobin (g/dL)	Platelets (x 10 ⁹ /L)	Sorafenib
Grade 1	≥ 1.5	< LLN – 10.0	≥75	Treat on time

				No change
Grade 2	≥ 1.0 to < 1.5	$< 10.0 - 8.0$	≥ 50 to < 75	Treat on time No change
Grade 3	≥ 0.5 to < 1.0	$< 8.0 - 6.5$	≥ 25 to < 50	Treat on time Reduce by one dose level
Grade 4	< 0.5	Life-threatening consequence; urgent intervention indicated	< 25	Delay sorafenib until toxicity resolves to Grade 2 or less then Reduce by two dose levels
Febrile Neutropenia				Sorafenib held until toxicity has resolved to Grade 2 or less; when sorafenib is restarted, reduce by one dose level

ANC - absolute neutrophil count ; AGC - absolute granulocyte count

- If no recovery after 30 day* delay, treatment should be permanently discontinued unless treating physician determines subject is deriving clinical benefit.
* Modify according to study specific cycle length.

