7.4 Safety

All subjects who receive at least one dose of study treatment will be valid for the safety analysis.

All observations pertinent to the safety of the study treatment will be recorded and included in the final report.

Safety variables include the following: AEs, laboratory changes (complete blood counts, electrolytes, chemistry, and coagulation), changes in vital signs (blood pressure, heart rate, respiratory rate, and temperature) and ECG at the investigator's discretion .

All AEs whether considered drug-related or not, will be reported in with a diagnosis, start/stop dates, action taken, whether treatment was discontinued, any corrective measures

taken, outcome, and other possible causes. For all events, the relationship to treatment and the intensity of the event will be determined by the investigator.

This trial will use the NCI-CTCAE v4.0 criteria for assessment of toxicity and SAE reporting with regard to toxicity grade.

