5	0.017	39.7 (40, 40)

If the trial continues to maximum accrual of 40 patients and maintains sufficient follow-up to observe 25 events (PD/death) with a median PFS of 4.1 months, then a 95% credible interval for median PFS would extend from 2.76 to 6.08 months.

Toxicity Monitoring

In addition, toxicity will be monitored closely in all patients using the method of Thall et al (1995). The interim monitoring will be first conducted after the first 20 patients have been evaluated and then be repeated after each cohort of 5 patients. Denote the probability of toxicity by θ_E , where toxicity is defined as any non-hematological Grade 3 or greater complications attributable to the treatment. We assume $\theta_E \sim \text{beta}(0.6, 1.4)$. We will stop the

trial if at any point $\Pr(\theta_E > 0.30 \mid \text{data}) > 0.85$. That is, we will stop the trial if, at any time during the study, we determine that there is more than 85% chance that the toxicity rate is more than 30%. Stopping boundaries corresponding to this stopping rule are listed in table 9.

Table 9: Stopping boundaries for toxicity monitoring

Among These Number of Patients	Recommend Stopping if Toxicity Observed in n or more patients
20	9
25	11
30	12
35	14

Table 10: The operating characteristics for toxicity monitoring are summarized in the following table

True toxicity probability	Probability of early stop	Sample size percentiles (10, 25, 50, 75, 90)
0.1	0.0001	40 40 40 40 40
0.2	0.017	40 40 40 40 40
0.3	0.211	25 40 40 40 40
0.4	0.651	20 20 25 40 40
0.5	0.938	20 20 20 20 30

Multc Lean V2.1 and OneArmTTE Version 4.1.1 were used for the trial design.

Futility monitoring in CTC website

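### The Section 8.1 toxicity rule never defines non-hematological, so a fatal or serious hematologic event may go uncounted and serious bleeding is ambiguous (low severity, one-sentence fix)

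*Combined protocol and SAP*

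**What the plan says.** Section 8.1 (Toxicity Monitoring) gives the toxicity probability a beta(0.6, 1.4) prior. It stops the trial if the posterior probability that the rate exceeds 0.30 is above 0.85, with looks at 20, 25, 30 and 35 patients. The monitored event is worded as follows: "toxicity is defined as any non-hematological Grade 3 or greater complications attributable to the treatment". No exception follows, and the protocol does not say which events are hematologic for this purpose.

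Two other places bear on the classification:

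- Table 2 (Section 6.2.1.2, hematologic toxicities) covers neutrophils, hemoglobin, platelets and febrile neutropenia. Grade 4 hemoglobin is described as "Life-threatening consequence; urgent intervention indicated". For febrile neutropenia the instruction is "Sorafenib held until toxicity has resolved to Grade 2 or less; when sorafenib is restarted, reduce by one dose level". The table governs sorafenib dosing only.
- The sorafenib event list in Section 2.3 puts hemorrhage under its hematologic heading, with Grade 3 at 2-3% and Grade 4 at up to 2%.

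Section 5.2 says that subjects who leave early because of toxicity count in the toxicity assessment. It does not mention the Section 8.1 rule or its event definition.

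The rule belongs to a "redesign, 20 patients have enrolled in study 2012-0870". For those first 20 patients, Section 1.1 reports that the investigators "found no grade 4 or 5 reactions".

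**The concern.** The rule helps decide whether up to 20 more patients are treated. As worded, an attributable Grade 3 laboratory value such as hypophosphatemia counts as one toxicity. An attributable death classed as hematologic counts as none. The same holds for febrile neutropenia and for a life-threatening Grade 4 hematologic event. Whether a serious bleed counts depends on which part of the protocol the person entering the data follows.

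Leaving laboratory cytopenias out is sound and is not questioned. Entry requires only "Hemoglobin ≥ 8.5 g/dL" and platelets of at least 60 x 10^9/L, and both limits already lie in the Grade 2 range of Table 2. The gap is the missing exception for fatal or clinically serious events, together with the undefined term.

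**Working it through.** **Inputs.** The prior, 0.30 limit, 0.85 cut-off, looks and boundaries are from Section 8.1 and Tables 9-10. The documents give no rate for the omitted events (call it h). I assume h = 1-2%, and also use 5%, which is the top of the listed hemorrhage rates (3% Grade 3 + 2% Grade 4). Let k be the number of counted toxicities in the first 20 patients.

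**1. Reproduce the plan.** The boundary at n is the smallest x with Pr(theta > 0.30 | Beta(0.6 + x, 1.4 + n - x)) > 0.85.

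| n | Boundary | Posterior at boundary | One event fewer |
|---|---|---|---|
| 20 | 9 | 0.906 | 0.807 |
| 25 | 11 | 0.918 | 0.838 |
| 30 | 12 | 0.863 | 0.764 |
| 35 | 14 | 0.883 | 0.801 |

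An exact binomial recursion over the four looks gives early-stop probabilities of 0.0001, 0.0168, 0.2114, 0.6512 and 0.9377 at true rates 0.1 to 0.5. Tables 9 and 10 are therefore correct, and the issue is one of definition only.

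**2. Effect of counting the omitted events, before any data.** If they are independent of counted events, the patient-level rate becomes 1 - (1 - 0.30)(1 - h).

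| h | Rate | Pr(stop early) |
|---|---|---|
| 0 | 0.300 | 0.211 |
| 1% | 0.307 | 0.237 |
| 2% | 0.314 | 0.265 |
| 5% | 0.335 | 0.354 |

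**3. What remains open.** Section 1.1 lists no Grade 4-5 reaction, febrile neutropenia or hemorrhage in the first 20 patients. Its one Grade 3 thrombocytopenia stays excluded under the fix. So k does not change, and only patients 21-35 can affect stopping, because the last look is at 35. The chance of at least one omitted event in those 15 patients is 1 - 0.99^15 = 0.140 to 1 - 0.98^15 = 0.261. In patients 21-25 it is 1 - 0.99^5 = 0.049 to 1 - 0.98^5 = 0.096.

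**4. One such event in patients 21-25, all other patients at 30%.** Let U be Pr(stop early) if the event patient adds 0 to the count, and C if that patient adds 1. If the patient cannot have another counted toxicity, the gain from the fix is C - U, which is the maximum. If the patient has an independent 30% chance of one, the baseline is 0.7U + 0.3C. At k = 8, for example, 0.7 x 0.333 + 0.3 x 0.623 = 0.420.

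| k | U | C | Baseline, independent | Gain, independent | Gain, maximum |
|---|---|---|---|---|---|
| 5 | 0.010 | 0.043 | 0.020 | 0.023 | 0.033 |
| 7 | 0.137 | 0.333 | 0.196 | 0.137 | 0.196 |
| 8 | 0.333 | 0.623 | 0.420 | 0.203 | 0.290 |

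k cannot be read from Section 1.1. Its non-hematological Grade 3 entries are AST 3, ALT 1, bilirubin 1, fatigue 2 and seven single events, which is 14 entries. Neither overlap between patients nor attribution is given.

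**The case against.** The strongest reply is that little is left uncounted. If bleeding is non-hematological, a fatal bleed already counts. A death from neutropenic infection may be coded as an infection and count as well. Section 5.2 can be read as bringing in anyone taken off study for toxicity, and death is a reason for withdrawal. Febrile neutropenia appears only in a dosing table and not among the expected or observed toxicities. A treatment-related death also calls for individual review more than for one unit in a tally.

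Much of this stands, and it is why the severity is low. It does not close the gap. Section 5.2 does not redefine the Section 8.1 event, and the replies about bleeding and sepsis rest on classification choices that the protocol leaves open.

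A reader might infer that hematologic harm goes unmonitored. The documents do not support that. SAEs go to the company within 24 hours (Section 7.4.1.4), and Section 7.4 states: "All observations pertinent to the safety of the study treatment will be recorded and included in the final report". Section 10 allows termination for safety findings, and mortality is estimated at the end. Any death is also a PFS event in the futility rule. That rule has a numeric threshold, but it tests efficacy and not attributable harm.

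A reader might also take the synopsis phrase "Assuming a 30% of grade 3 or 4 treatment related toxicity rate" as support for a 30% limit on a broader event. It illustrates confidence-interval width in the 20-patient descriptive plan and sets no tolerability limit.

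**Conclusion.** The definition should be tightened, at low severity. Read literally, the rule gives no weight to attributable hematologic deaths, febrile neutropenia or Grade 4 hematologic SAEs, and it leaves serious hemorrhage undetermined.

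The expected effect is about 3 to 5 percentage points on early stopping at a 30% counted rate if h is 1-2%. It is about 14 points at 5%, which is relevant if hemorrhage would otherwise have been left out. These are before-data figures that apply h to all looks, although the count in the first 20 is already fixed. A single event is influential only if k is near the boundary of 9. The larger gains of 0.20 to 0.29 require that the patient could have had no other counted toxicity, so 0.14 to 0.20 is the fairer range for k = 7 to 8. At k = 5 or below the gain is about 0.03 or less.

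The conclusion rests on assumed event rates and an unreported k. A reader might infer that the final toxicity rate has the same omission. The secondary analysis does not restate the definition, so that is not established.

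**What to change.** In Section 8.1, define toxicity as any of the following attributable to treatment:

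- (a) a non-hematological event of Grade 3 or higher, expressly including hemorrhage of Grade 3 or higher;
- (b) a Grade 5 event of any type;
- (c) febrile neutropenia, or a Grade 4 hematologic event reported as an SAE.

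Keep isolated laboratory cytopenias excluded, in line with Section 7.4.1.4. State that the same definition applies to the final toxicity rate, its 90% credible interval and the posterior probability that it exceeds 30%. Leave the prior, the 0.30 limit, the 0.85 cut-off and Table 9 unchanged.

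Naming hemorrhage is a substantive part of the change, given how Section 2.3 classifies it, and should be presented as such.

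The cost is one sentence, using adverse-event data already collected, with no new visits, patients or boundaries. There are two downsides. Early stopping becomes slightly more likely, by the amounts shown above. Some investigator judgement also enters, because the SAE criteria include medically important events. Using the classification already made on the SAE report limits the second.
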